## **4.5 Safety Monitoring Committee**

A Safety Monitoring Committee (SMC) comprised of an independent DEB specialist, enrolling PIs, and Sponsor representatives and/or designee(s) hold periodic teleconferences to evaluate subject safety and treatment status. An SMC charter dictates procedure, responsibilities, membership, data requirements and meeting timing. A written summary documenting the results and recommendations of each review is provided to the investigator(s) and maintained on file with the Sponsor. Additional sub-investigators and scientific personnel may participate in reviews, as appropriate. The SMC provides recommendations about stopping or continuing the trial and has the authority to recommend dose or regimen modifications for safety concerns. The SMC may also make recommendations regarding the selection or retention of participants, their management, improving adherence to protocol-specified regimens, and the procedures for data management and quality control.

## **4.6 Subject Companions**

Subjects are permitted to bring a companion to study visits. Costs associated with travel to the Investigative Site, including those of a companion, are reimbursed by the sponsor.

## 5 Study Procedures

### 5.1 Stopping Criteria

**Table 1** provides the stopping criteria. Occurrence of any of these observations triggers a temporary suspension of KB103 administration pending a safety investigation.

**Table 1 - KB103-001 Stopping Criteria**

Event	Severity	Number of Events
A treatment emergent serious adverse event that is definitely or suspected to be related to KB103.	Any	1
An AE associated with HSV infection in combination with a positive RCV qPCR assay result.	Any	1
An immune response determined by the Investigator to be possibly, probably or definitely related to investigational product or a procedure.	Severe	1
Any treatment emergent systemic infection designated as possibly, probably or definitely related to investigational product or a procedure.	Moderate or higher	2 or more
A treatment emergent uncontrolled bacterial, viral, or fungal infection in an area administered investigational product where product sterility testing results reported post injection were positive for contamination.	Mild or higher	1

For subject safety, subjects should be followed in accordance with the study visits and procedures as outlined in the protocol. An occurrence of any of these safety observations is shared with the SMC and the appropriate authorities. The SMC reviews the results of the safety investigation and may request any additional data needed to assess the safety of restarting product administration. The SMC determines if the suspension can be lifted or if the trial terminates based on their review of the safety investigation.

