### **4.3 Concomitant Therapy and Skin Care**

Stanford is a major epidermolysis bullosa center and has an established multidisciplinary epidermolysis bullosa team. Subjects will have full access to the care provided by this team throughout participation in this study.

The Investigator is encouraged to restrict topical administration of any EB therapy to a wound that receives KB103 or placebo for a minimum of 72 hours following administration. Any therapy administered to the target wound should also be applied to the control wound. Throughout the study, any concomitant medications or treatments deemed necessary to provide adequate supportive care may be prescribed. In particular, medication should be considered during and after any biopsies to treat pain and/or anxiety (i.e. lidocaine, lorazepam, etc.). Routine skin care for DEB patients continues throughout the study. Though not anticipated due to the non-replicating nature of KB103, active herpes should be treated with an antiviral at the discretion of the Investigator.

Conscious sedation to anesthetize pain associated with biopsies is acceptable at the discretion of the Investigator.

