### 5.3.3 Screening and Baseline Procedures

The following procedures are performed on or the day before the first planned administration day.

- Review and signature of informed consent form
- The following evaluations are required only if RDEB diagnosis documentation is not available to support entry into this protocol. If these are needed, the screening visit may occur several weeks prior to the baseline visit:
  - Collection of a biopsy for EM/IEM
  - Collection of a biopsy for IF
  - Collection of blood for genetic testing
- Collection of demographic data (e.g. sex, age, race, and ethnicity)
- Inclusion/exclusion criteria
- Medical history and medication history
- Collection of blood (approximately 15 mL) for clinical laboratory tests:
  - Serum chemistry
  - Hematology
  - HIV, Hep B, Hep C
  - Baseline viral shedding
  - Baseline HSV and COLVII autoantibodies
- Collection of urine
  - For a pregnancy test, if applicable
  - For baseline viral shedding
- Physical and skin exam
- Vital signs: blood pressure, heart rate, respiratory rate, temperature
- Collection of a baseline skin swab for viral shedding analysis
- Bacterial culturing of target wounds (if clinical evaluation is indicative of infection)
- Digital imaging of target areas
- Collection of a biopsy from intact skin for IF and IEM analyses. This collection can occur at a later visit at the discretion of the Investigator.
- Patient reported outcomes (PRO) questionnaire
- Investigator's global assessment

## 5.4 Cycle 1

The patient will visit the Investigative site for the first dose of Cycle 1. Additional Cycle 1 doses can occur on-site or at-home at the discretion of the Investigator. Unless the patient requires disease characterization, Day 1 of Cycle 1 is the same day as the Screening/Baseline visit. For Cycle 1, KB103 and placebo are administered topically every 2 to 3 days to correspond with bandage changes, up to 3 months.

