### 5.4.2 At-home Procedures

After the first administration of each cycle, KB103 may be administered at home by a caretaker every 2 to 3 days until wound closure, a stopping criterion is met, 3 months have elapsed, or until directed to discontinue by the Investigator.

Appendix 1 provides administration instructions. Wound closure is monitored through remote imaging.

### 5.4.3 Last Dosing Day of Cycle 1

The patient will visit the Investigative site on or near the final Cycle 1 administration day, in which the following procedures will be performed:

- Collection of blood (approximately 10 mL) for clinical laboratory tests:
  - Serum chemistry
  - Hematology
  - Viral shedding
  - HSV and COLVII autoantibodies
- Collection of urine for viral shedding
- Optional: biopsy collection from a wound area
- Wound stenciling
- Topical administration of KB103 and placebo to the target areas

## 5.5 Observation Period (OP) 1

Following Cycle 1 wound closure and/or 3 months, the patient returns home. Wound areas are imaged every 2 to 3 days at home with a phone app.

The duration of OP 1 varies. If complete wound closure is obtained during Cycle 1, OP 1 ends when the wound(s) re-open. If complete closure is not obtained during Cycle 1, OP 1 ends when the wound surface area increases relative to size of the wound at the last Cycle 1 administration.

## 5.6 Cycle 2

The patient will visit the Investigative site for the first dose of Cycle 2. Additional Cycle 2 doses can occur on-site or at-home at the discretion of the Investigator. For Cycle 2, KB103 and placebo are administered topically every 2 to 3 days to correspond with bandage changes, up to 3 months.

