### 5.7.1 OP 2 Monthly Visits

At 30-day intervals (+/- 7 days) after the last administration of Cycle 2, the patient returns to the clinic for follow-up procedures:

- Adverse events
- Concomitant medications
- Vital signs
- Digital imaging of wounds
- PRO assessment
- Investigator's global assessment
- Collection of blood (approximately 10 mL) for clinical laboratory tests:
  - Serum chemistry
  - Hematology
  - Viral shedding
  - HSV and COLVII autoantibodies
- Collection of a skin swab for viral shedding analysis
- Collection of urine for viral shedding
- Month 3 only: physical exam
- Optional: Biopsy from a wound administered KB103 or placebo
- Wound stenciling
- If a target wound is open: Topical administration of KB103 and placebo to the target areas.

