## 9 Adverse Events

Throughout the course of the study (from the date of informed consent), all adverse events (AEs) will be monitored and reported on the AE case report form. If an adverse event occurs, the first concern will be the safety of the study participants. All AEs occurring after administration will be followed throughout the study. All AEs related to study treatments or procedures will be followed until resolved or stabilized or until follow-up is no longer possible.

In general, even when not participating in a clinical trial, the study subjects and their caretakers communicate with their EB doctor on a regular basis via phone. Study subjects and their caretakers will be instructed to report via phone any adverse events that occur during the study while off-site. The events will then be transcribed to the AE CRF.

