### 10.6.1 Adverse Events

Adverse events are coded using the MedDRA adverse event dictionary. Safety evaluations are based on occurred adverse events, laboratory values, vital signs and appearance of collagen VII antibodies, and RCV. Severities of toxicities is described using the NCI Common Toxicity Criteria (CTC) grades.

Adverse events are grouped into pre-treatment adverse events and treatment-emergent adverse events and are tabulated by preferred terminology and by body system for each study phase. The number of adverse event entries, as well as the number of patients are reported. Analyses include tabulation of adverse event type, relationship to KB103, seriousness, and severity of adverse events according to CTCAE.

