### 10.6.4 Laboratory Tests

Laboratory test values are presented in shift tables and by display of changes to baseline. Evaluations of collagen VII antibodies and RCV will be done descriptively.

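### Stopping criterion row 2 and the planned RCV evaluation depend on an RCV qPCR result that no procedure in protocol version 4.0 orders

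*Protocol*

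**What the plan says.** Protocol Table 1 lists five events, any of which temporarily suspends KB103 while safety is investigated. Row 2 needs one event of any severity: "An AE associated with HSV infection in combination with a positive RCV qPCR assay result". The analysis sections expect RCV data as well. Section 10.6.1 states that "Safety evaluations are based on occurred adverse events, laboratory values, vital signs and appearance of collagen VII antibodies, and RCV", and Section 10.6.4 that "Evaluations of collagen VII antibodies and RCV will be done descriptively".

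On herpes itself, Section 4.3 says it is not anticipated, because the vector does not replicate, but that "active herpes should be treated with an antiviral at the discretion of the Investigator". It gives no instruction to take a sample.

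Much of the dosing may happen away from the clinic. Section 5.4.2 provides that "KB103 may be administered at home by a caretaker every 2 to 3 days until wound closure, a stopping criterion is met", or until 3 months have passed or the Investigator directs a stop. Section 5.6.2 repeats this for Cycle 2. For events away from the site, Section 9 says: "Study subjects and their caretakers will be instructed to report via phone any adverse events that occur during the study while off-site".

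Virological samples are collected. Section 5.7.1 includes "Collection of a skin swab for viral shedding analysis", with blood and urine for shedding, and Section 5.8 lets any of the monthly procedures be done at an unscheduled visit. Section 8.1 names these sample types but no assay.

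**The concern.** Row 2 is a conjunction: an HSV-associated adverse event and a positive RCV qPCR. If the second element is never measured, the row is not met, whatever the subject's true state. An unmet row could then be read as reassurance when it only records that no test was done.

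Row 2 is also the only row that names HSV or RCV, which is the hazard specific to a replication-deficient HSV vector. It is meant to act on the first event at any severity. It is one of the written conditions for ending home dosing, so a caretaker's dosing could continue after an HSV-type event while that condition stayed undetermined. The RCV evaluation planned in Section 10.6 would likewise have no ordered source of data in subjects treated under version 4.0.

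**Working it through.** The plan states no figure here, so the check is to trace where an RCV result could come from and what else would stop dosing.

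**Step 1: every mention of RCV in the protocol.**
- Abbreviations list: definition only.
- Section 1.4: a screen of a purified virus stock, which is a product test and not a subject sample.
- Table 1, row 2: uses a result.
- Sections 10.6.1 and 10.6.4: use a result.

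Three places use an RCV result in subjects, and none produces one.

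**Step 2: where an order for the test would be expected.**
- Table 2, and the version 4.0 schedule in SAP Appendix 1: rows for viral shedding (skin swab; blood and urine), HSV antibody and COL7 antibody. There is no RCV row. A for-cause test need not sit in a visit schedule, so this absence alone proves little.
- Visit lists in Sections 5.3.3, 5.4.1, 5.4.3, 5.6.1, 5.6.3 and 5.7.1: shedding samples and antibody tests, no RCV.
- Section 8.1: blood, urine and swabs for shedding, no assay named, no mention of RCV or qPCR.
- Sections 8.5.1 to 8.5.4: chemistry and hematology, pregnancy test, HSV antibody, collagen VII antibody. HSV antibody is serology and cannot stand in for an RCV qPCR.
- Section 4.3: antiviral only.
- SAP Section 9.4: outputs for shedding and the two antibody assays, none for RCV.

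The version 4.0 text therefore names no sample designated for RCV qPCR, no trigger for ordering it and no timepoint. The text missing from the public file lies before the contents list, in the results for subjects 01 and 02, and at the front of the SAP. None of it falls in the procedure or laboratory sections.

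**Step 3: would another row catch the event?** Take one non-serious HSV-associated adverse event.
- Row 1 needs a serious event suspected or known to be related. Not met.
- Row 3 needs a severe immune response. Not met.
- Row 4 needs at least two related systemic infections of moderate or greater severity. Not met by one event.
- Row 5 needs an infection together with a positive product sterility result. Not met unless product was contaminated.

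Only row 2 addresses this event.

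**Step 4: follow the event through the text.** The subject is dosed at home. The event is phoned in (Section 9). The Investigator may prescribe an antiviral (Section 4.3). The at-home sections list no sampling. In the version 4.0 schedule, blood and urine for shedding fall at baseline, at the last dose of each cycle and at the later monthly visits, so none is due between first and last dose of a cycle. Row 2 stays undetermined, and dosing continues unless someone chooses to stop it. Every step complies with the protocol.

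**The case against.** The best reply is that the material for the test exists. Swabs, blood and urine are collected on schedule and may be taken at an unscheduled visit. The unnamed shedding assay may itself be the RCV qPCR, and the SMC charter, which sets data requirements and is not among the documents, may order it. Row 2 can also be read as implying a for-cause test. Section 9.1.1 provides for medical tests as appropriate to document that events have resolved. Section 9.4.1 requires close monitoring of the wounds, Section 6.1 has the Investigator guide home dosing from images, and Section 6.6 gives subjects direct phone access.

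Other protections remain. Row 1 reaches important medical events suspected to be related, because the definition of serious in Section 9.1.2 includes them. The Investigator can direct that dosing stop, the Investigator or Sponsor can withdraw a subject, and the SMC can recommend regimen changes. This is a single-site cohort of 3 planned subjects.

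Most of this stands, and it lowers the priority. It does not close the gap. No sentence connects shedding samples to RCV, and the version 1.0 schedule in the SAP listed RCV evaluation separately from the shedding assays, which suggests that they were distinct items. Section 8.1 describes swabs at areas given KB103, so a lesion elsewhere is not clearly covered. The testing provision in Section 9.1.1 concerns resolution and names no assay. In Section 5.1 the SMC's request for further data comes when it reviews a suspension already triggered.

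A reader might infer more: that version 4.0 collects no usable virological sample, that row 2 can never be met, or that dropping the version 1.0 row was a mistake. The documents support none of these. Sampling exists, a site may test on its own initiative, and a difference from a superseded version is not an error in the current one.

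**Conclusion.** The point holds as a gap between a rule and the procedure that should feed it. One of five stopping rows, and the RCV evaluation in Section 10.6, rely on a result that version 4.0 does not order. The exposed case is a single non-serious HSV-associated adverse event, most plausibly one reported by phone during at-home dosing. There, suspension depends on individual judgement and not on the stated criterion.

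The probability of such an event cannot be estimated from the documents. Section 1.6 reports no KB103-related adverse events in the four subjects treated under version 2, which is too few to exclude an uncommon one. The conclusion assumes that neither the shedding assay nor the SMC charter already provides an event-driven RCV qPCR. If one does, only a clarifying statement is missing. Priority is low to moderate: the consequence is limited, but the rule concerns the vector's specific hazard and the repair is cheap.

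**What to change.** State in Sections 4.3 and 8.1 that any suspected HSV-associated adverse event triggers an RCV qPCR. Use whichever shedding sample type is validated for that assay; the documents do not show which one that is, so the sponsor should name it. Collect the sample at an unscheduled visit, before antiviral treatment where feasible, and hold KB103 until the result is known. If the shedding assay already is the RCV qPCR, say so in Section 8.1 and still add the trigger.

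The cost is a few sentences, an occasional assay, a small sample, possibly one extra visit for a subject dosed at home, and a short dosing delay. If blood is the validated sample, the draw must be weighed against the aim in Section 8.5.1 of keeping blood collection low. Because Section 6.5 ties placebo dosing to KB103 dosing days, holding KB103 in all of a subject's treated areas would pause placebo too, so the paired wounds would miss the same dosing days.

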### 5.2 Study Schedule

Study visit procedures are performed only after a signed informed consent / assent is obtained. During the study, every effort should be made to adhere to the visit schedule provided in the Schedule of Events (**Table 2**). Visit windows for each visit are described below.

Patients visit the clinic at baseline and as needed after baseline for the Cycle 1 and Cycle 2 dose administrations. After the first dose administration of each cycle, patients can either return to the clinic for additional administrations or the administrations can occur at home by a trained professional. During the on-site dose administration periods, patients will stay in lodging near the clinical site. Following the 2nd cycle, patients will return home and visit the clinic at least monthly for 3 months. Interim unscheduled visits may occur in between the monthly visits depending on the patient's ability and willingness to travel.

**Table 2 - Schedule of Events**

Procedures	Screen/ BL	Cycle #1		OP  #1	Cycle #2		OP #2			LTFU
		Dosing every 2-3 days	Home images		Dosing every 2-3 days	At-home monitoring and monthly on-site visits	C2 +1mo	C2 +2mo	C2 +3mo	
		≤ 3 months	Variable		≤ 3 months	3 months after C2 				
Urine Pregnancy Test	X									
HIV, Hep B, Hep C Testing	X									
Hematology & Chemistry 	X		X			X	X	X	X	
COL7 Antibody Assay	X		X			X	X	X	X	
HSV Antibody Assay	X		X			X	X	X	X	
Wound Area Assignment	X									
Pre-dose Tattoos	X									
Concomitant Medications	X	X	X		X	X	X	X	X	
Adverse Events	X	X	X		X	X	X	X	X	
Viral shedding (skin swab)	X	X	X		X	X	X	X	X	
Viral shedding (blood and urine)	X		X			X	X	X	X	
Physical Exam	X								X	
PRO Assessment	X	X	X		X	X	X	X	X	
Global Wound Assessment	X	X	X		X	X	X	X	X	
Vital Signs	X	X	X		X	X	X	X	X	
At-home wound imaging 		X	X	X	X	X	X	X	X	
On-site wound imaging	X	X	X		X	X	X	X	X	
Wound stenciling	X	X	X		X	X	X	X	X	
IP Administration	X	X	X		X	X	X	X	X	
Wound biopsy 	X		X			X	X	X	X	

 OP = Observation Period Visit windows for the OP2 visits are +/- 1 week After screening/baseline, performed only as clinically indicated to minimize blood draws At-home wound imaging occurs throughout the study during bandage changes Biopsies are performed at the discretion of the Investigator and Sponsor.

## 5.3 Screening and Baseline

For well-characterized subjects that meet criteria, the procedures for screening and baseline will be conducted during the same visit to the investigative site as the first day of Cycle 1. Subjects that are not well-characterized may be screened well in advance (about 2 months) of the planned baseline to allow time for genetic testing.

### 5.3.1 Informed Consent

The Investigator is responsible for obtaining an ICF signed by the subject or legally authorized representative from every subject prior to his/her participation in the study, in accordance with the Code of Federal Regulations (CFR), Title 21, Part 50.20. For subjects between the ages of 7 and 17 (inclusive), the Investigator is responsible for obtaining assent from the subject and consent from both parents or legal guardians. For subjects that are 5 or 6 years old, the Investigator is responsible for obtaining parental/legal guardian consent (no assent is required).

The ICF/Assent that is used must be the current version and must be approved by both the reviewing IRB and by the Sponsor. Informed consent/assent is obtained from the subject after a full explanation of the purpose of the study, risks and discomforts involved, potential benefits, etc. have been provided by the Investigator both verbally and in writing. The original signed copy of the informed consent/assent must be maintained in the institution's records, and is subject to inspection by a Sponsor representative.

### 5.3.2 Phone Screening

A phone screen is utilized to minimize subject travel. An Investigator or designee will prescreen medical histories of RDEB patients for potential inclusion into this study. Potential subjects or parent or guardian are contacted by phone. An Investigator or designee provides a study overview, key inclusion/exclusion criteria, information about the recruitment process, and addresses questions. If the potential subject remains interested in participating in the study, a copy of the informed consent is sent to the potential subject to review.

Medical information reviewed may include the following and is dependent upon the Investigative Site's receipt of prior authorizations to access the data:

- NC1 and LH24 antibody results
- Genetic testing results, including COL7A1 genotype of the subject
- COL7 antibody history
- IF and EM/IEM results
- Medical history

The Investigator may request additional personal health information disclosure authorizations from the potential subject to assist with Screening.

